**Patient's Global Impression of Change (PGIC) of VLS**

PGIC in Worst Itch (WI), Worst Pain (WP) and Worst Penetrative sex related Pain (WPP) must be reported to the clinical staff at Week 4, Week 8, and Week 12 (or EoT) visits using a 7-item verbal rating scale:

Please choose the response below that best describes the overall change in your [Worst Itch\*] associated with your lichen sclerosus since you started applying the trial medication:

- Very much better
- Much better
- A little better
- No change
- A little worse
- Much worse
- Very much worse

\*Repeat with Worst Pain and Worst Penetrative sex related Pain.

#### **Patient's rating of importance of improvements of VLS**

Patients reporting an improvement in PGIC (i.e., 'Very much better', 'Much better' or 'A little better') must report the importance of the improvement at Week 4, Week 8, and Week 12 (or EoT) visits using a 2-item Importance Questionnaire:

Question 1: You have reported an improvement in your [Worst Itch\*] associated with your lichen sclerosus since you started applying the trial medication. Was the improvement important to you? (Yes/No). If yes, please proceed to question 2.

Question 2: In which way(s) was the improvement in your [Worst Itch\*] associated with your lichen sclerosus important to you? (Free text).

\*Repeat with Worst Pain and Worst Penetrative sex related Pain.

#### **Menopausal status and Menstrual cycle status**

Menopausal status (Pre-menopausal or Menopausal) will be recorded for all women, while menstrual cycle status (i.e., whether the patient is menstruating or not, reason in case of no menstruation, number of days since the first day of the latest menstruation period, average duration of menstruation period in days, regularity of menstrual cycle) must be evaluated by all pre-menopausal women; both statuses will be reported at Baseline, and Week 12 (or EoT) visits.

#### **International Consultation on Incontinence Questionnaire Urinary Incontinence Short Form (ICIQ-UI-SF)**

Incontinence status must be evaluated by the patient at Baseline and Week 12 (or EoT) visits using the ICIQ-UI-SF questionnaire.

The ICIQ-UI-SF is a validated questionnaire with a recall period of 4 weeks comprising a total of 4 questions about when, how often and how much urine is leaked and how much urine leaking interferes with everyday life. The ICIQ-UI-SF score ranges from a maximum score of 21 (indicating maximum burden) and a minimum score of 0 (indicating no burden). A score  $\geq 1$  indicates urinary incontinence [6].

The ICIQ-UI-SF sum score is the sum of items 3-5 as follows:

Item 3. *How often do you leak urine?* (0=never; 1=about once a week or less; 2=two or three times a week; 3= about once a day; 4=several times a day; 5=all the time)

Item 4. *We would like to know how much urine you think leaks. How much urine do you usually leak?* (0=none; 2=a small amount; 4=a moderate amount; 6=a large amount)

Item 5. Overall, how much does leaking urine interfere with your everyday life? Please ring a number between 0 (not at all) and 10 (a great deal) (0-10).

Item 6 is the self-diagnostic question for type of UI and is not included in the final score:

*When does urine leak? (please tick all that apply to you) (never, urine does not leak; leaks when you cough or sneeze; leaks when you are asleep; leaks when you are physically active/exercising; leaks when you are finished urinating and are dressed; leaks for no obvious reason).*

### Skindex-29

Skindex-29 is a skin specific multidimensional quality-of-life instrument. It must be evaluated by the patient, concentrating on their vulvar area, at Baseline, Week 4, Week 8, and Week 12 (or EoT) visits using the Skindex-29 Quality of Life Index questionnaire. It inquires how often (1. Never, 2. Rarely, 3. Sometimes, 4. Often, 5. All the time) during the previous 4 weeks the patient experienced the effect described in each item. Seven items address the Symptoms domain, ten items the Emotions domain, and twelve items the Functioning domain. All responses are transformed to a linear scale of 100, varying from 0 (no effect) to 100 (effect experienced all the time) as 25 times (score-1). Skindex-29 scores are reported as three scale scores, corresponding to the three domains; a scale score is the average of a patient's non-missing responses to items in a given domain [7]. The questionnaire comprises 30 items; however, Item 18 is excluded from the Skindex-29 score as per the guidelines of the originators of the test. If any scale has more than 25% of the responses missing, the scale is missing.

Table 1 Skindex-29 domains and their items

Functioning	Emotions	Symptoms
2. MSC affects how well I sleep	3. I worry that MSC may be serious	1. My skin hurts
4. MSC makes it hard to work or do hobbies	6. MSC makes me feel depressed	7. MSC burns or stings
5. MSC affects my social life	9. I worry about getting scars from MSC	10. My skin itches
8. I tend to stay at home because of MSC	12. I am ashamed of MSC	16. Water bothers MSC (bathing, washing hands)
11. MSC affects how close I can be with those I love	13. I worry that MSC may get worse	19. My skin is irritated
14. I tend to do things by myself because of MSC	15. I am angry about MSC	24. My skin is sensitive
17. MSC makes showing affection difficult	21. I am embarrassed by MSC	27. MSC bleeds
20. MSC affects my interactions with others	23. I am frustrated by MSC	
22. MSC is a problem for the people I love	26. I am humiliated by MSC	
25. MSC affects my desire to be with people	28. I am annoyed by MSC	
29. MSC interferes with my sex life		
30. MSC makes me tired		

MSC = My skin condition

### VQLI

The Vulvar Quality of Life Index (VQLI) questionnaire is a vulvar specific quality-of-life instrument. It must be evaluated by the patient at Baseline, Week 4, Week 8, and Week 12 (or EoT) visits.

The questionnaire comprises a total of 15 questions with a recall period of 1 month under the following domains:

- Symptoms (Questions 1–2)
- Feelings and Emotions (Questions 3–5)
- Activities of daily living (Questions 6–10)
- Relationships (Question 11)

- Sexual function (Questions 12–13);
- Future health concerns (Question 14)
- Treatment (Question 15).

Each of the questions are graded zero to three on a Likert scale, with 0 representing no symptom or complaint ('Not at all' or 'Not applicable'), 1 ('A little'), 2 ('A lot') and 3 ('Very much'). The individual domain scores are the sum of the respective item scores (coded 0-3), while the total score is the sum of all 15 items, ranging from 0 to 45 [8].

### **VLS patient journey sheet**

The Burden of living with VLS before entering the trial must be described by the patient by filling in the 'VLS patient journey sheet' at the Screening 1 visit. The patient journey sheet is a questionnaire which collects information about:

- which issues the VLS patient has experienced in relation to VLS within four areas: symptoms, psychological impacts, social impacts, and functional impacts (the issues are entered as free text)
- the patient can name up to four of the issues experienced in relation to VLS they have found most burdensome.

### ***Clinician reported outcomes (ClinRO) assessments***

#### **Vulvar lichen sclerosus Area and Sign Severity Index (VASSI)**

The Vulvar lichen sclerosus Area and Sign Severity Index (VASSI) evaluates the severity of 3 non-permanent signs of VLS in 5 different vulvar areas. It will be performed at Screening 1, Baseline, Week 1, Week 4, Week 8 and Week 12 (or EoT) visits for all patients.

**Areas:** The 5 different vulvar areas are Clitoris and periclitoral skin (**C**), Right interlabial sulcus and labium minus (**R**), Left interlabial sulcus and labium minus (**L**), Posterior fourchette and perineum (**P**), Anus and perianal skin (**A**))

**Signs:** The 3 non-permanent signs of VLS are **Fissures/erosions** (longitudinal/patchy ruptures of the skin surface), **Ecchymoses** (bleedings within the skin) and **Hyperkeratoses** (patches/plaques of bright white skin with a 'powdery' texture).

**Severity:** The severity must be scored on a 4-point scale from 0-3 (i.e., 0 (no lesion), 1 (length of lesion  $\leq$  5 mm), 2 (length of lesion  $>$  5mm and  $\leq$  10 mm) or 3 (length of lesion  $>$  10 mm)) for each non-permanent sign in each vulvar area (i.e., the light grey cells in [Table 2](#)). For endpoint analyses, the VASSI Area scores, VASSI Sign scores and Total VASSI score (i.e., the white cells in [Table 2](#)) will be calculated as follows:

1. A VASSI Area score (**VASSIC, -R, -L, -P, -A**) is calculated by summing up the 3 severity scores for Fissures/erosions, Ecchymoses and Hyperkeratoses in the particular vulvar area [range 0-9].
2. A VASSI Sign score (**VASSIF, -E, -H**) is calculated by summing up the severity scores for a particular sign across all 5 vulvar areas [range 0-15]
3. The Total VASSI (**VASSI**) score is calculated by summing the 5 VASSI Area scores or 3 VASSI Sign scores [range 0-45]

Table 2 Vulvar lichen sclerosus Area and Sign Severity Index (VASSI)

Signs	Vulvar areas					VASSI Sign scores
	Clitoris and periclitoral skin (C)	Right interlabial sulcus and labium minus (R)	Left interlabial sulcus and labium minus (L)	Posterior fourchette and perineum (P)	Anus and perianal skin (A)	
Fissures erosions (F)						VASSI F
Ecchymoses (E)						VASSI E
Hyperkeratoses (H)*						VASSI H
VASSI Area scores	VASSI C	VASSI R	VASSI L	VASSI P	VASSI A	Total VASSI score

Light grey cells must be filled in by the investigator with severity scores. The severity must be scored on a 4-point scale (i.e. 0 (no lesion), 1 (length of lesion  $\leq$  5 mm), 2 (length of lesion  $>$  5 mm and  $\leq$  10 mm) or 3 (length of lesion  $>$  10 mm) for each non-permanent sign in each vulvar area; White cells will be calculated.

### Clinician's Global Assessment (CGA) of VLS

The Clinician's Global Assessment (CGA) of VLS evaluates the global (overall) severity of VLS in the entire vulvar region (i.e., including the clitoris, periclitoral skin, interlabial sulci, labia minora, posterior fourchette and perineum, anal and perianal areas). The CGA will be evaluated on a 5-point scale ranging from Clear to Severe at Screening 1, Baseline, Week 1, Week 4, Week 8, and Week 12 (or EoT) visits, using the following Table 3 below:

Table 3 Clinician's Global Assessment (CGA) of VLS

CGA Score	Description
Clear	No visible Non-permanent signs* of VLS (Fissures/Erosions, Ecchymoses or Hyperkeratoses) in the vulvar region. Note: Permanent signs# of VLS may be present
Almost clear	Barely visible Non-permanent signs* of VLS (Fissures/Erosions, Ecchymoses or Hyperkeratoses) in the vulvar region.
Mild	Slightly visible Non-permanent signs* of VLS (Fissures/Erosions, Ecchymoses or Hyperkeratoses) in the vulvar region
Moderate	Easily visible Non-permanent signs* of VLS (Fissures/Erosions, Ecchymoses or Hyperkeratoses) in the vulvar region.
Severe	Markedly visible Non-permanent signs* of VLS (Fissures/Erosions, Ecchymoses or Hyperkeratoses) in the vulvar region

\*Non-permanent signs of VLS include fissures/erosions (longitudinal/ respectively patchy ruptures of the skin surface), ecchymoses (bleedings inside the skin) and hyperkeratoses (patches/plaques of bright white skin with a 'powdery' texture). Hyperkeratoses must be distinguished from Sclerosis (areas of yellowish/ivory white skin with a smooth/waxy/firm texture) and pallor (areas of pale whitish skin that differ from hyperkeratosis in that they are not "powdery")

# Permanent signs of VLS include e.g., atrophy, sclerosis, pallor, scarring or fusion.

### Clinician's Global Impression of Change (CGIC) of VLS

Clinician's Global Impression of Change (CGIC) in non-permanent signs of VLS including fissures/erosions (longitudinal/respectively patchy ruptures of the skin surface), ecchymoses (bleedings inside the skin) and hyperkeratoses (patches/plaques of bright white skin with a 'powdery' texture) will be assessed at Week 1, Week 4, Week 8, and Week 12 (or EoT) visits using the below 7-item verbal rating scale.

The possible responses are as follows:

- Very much better
- Much better

- A little better
- No change
- A little worse
- Much worse
- Very much worse

## 2.4.2 Safety and Tolerance

### Adverse Events

All adverse events (AE) are recorded with the following attributes:

- Start and End dates
- Ongoing status
- Date site aware of AE
- Severity (mild, moderate, severe)
- Relationship to study drug (not related, unlikely related, possibly related, probably related)
- Action taken with study drug (not changed, temporarily interrupted, withdrawn, not applicable – no study drug, unknown)
- Outcome (fatal, not recovered/not resolved, recovered/resolved, recovered/resolved with sequelae, recovering/resolving, unknown)
- Recovered/resolved with sequelae specified (free text)
- Was medication given to treat this AE?
- Serious AE (SAE)
- Criteria for SAE (death, life-threatening, inpatient hospitalisation or prolongation of existing hospitalisation, congenital anomaly or birth defect, important medical event)

Any AE is treatment-emergent, if fulfilling the definition in Section 4.4.5.

Any AE is a drug-related AE, if relationship to IMP is not assessed as *not related*.

Any AE is leading to drug withdrawal, if action taken with IMP is *drug withdrawn*.

Verbatim terms of the description of AEs will be coded according to MedDRA version 27.0 and classified according to primary system organ classes (SOC) and preferred term (PT).

### Laboratory Parameters

There will be no scheduled sampling for clinical laboratory analyses in this trial, apart from the urine pregnancy tests mentioned below.

If there is a suspicion of a medical condition (considered related or not to the IMP), relevant laboratory samples may be taken and analysed at the discretion of the investigator; none of these samples will be stored for future analysis.

During the course of the trial, urine pregnancy tests will be performed at Screening 1, Baseline, Week 1, Week 4, Week 8, Week 12 (or EoT) visits, and at the follow-up visit (Week 14), if it is an in-clinic visit.

### Vital Signs

Vital signs (systolic blood pressure, diastolic blood pressure, heart rate and temperature) will be recorded at Baseline (Week 0) and Week 12 (or Early termination (EoT)) visits. Vital signs are also recorded at Week 14 (Follow-up) if judged necessary by the investigator, and if it is an in-clinic visit. Any abnormalities must

be assessed as “clinically significant” or “not clinically significant” by the investigator. If a vital sign is both abnormal and clinically significant, an AE event must be reported.

### **Physical Examination**

A complete (i.e., including all body systems as well as the vulvar region) physical examination is required at Screening 1 and Week 12 (or EoT) visits. An abbreviated physical examination (including the vulvar region as minimum; other body systems may be included depending on present signs, symptoms, or investigation outcomes) is required at the Baseline visit (and if judged necessary by the investigator) at the FU visit.

Any abnormalities must be assessed as either “clinically significant” or “not clinically significant” by the investigator. If a physical examination is both abnormal and clinically significant, an AE event must be reported.

### **2.4.3 Drug Accountability, Extent of Exposure and Study Treatment Compliance**

Patients will at visit 6, visit 8 and visit 10 be asked to return the dispensed carton box with the used and unused tubes. All returned boxes with used and unused tubes will be weighed together to determine the amount of IMP used. The calculations for drug used will use: a) a carton box packed with 8 full labelled tubes weighs on average 658.112 g; b) a full labelled tube weighs on average 73.928 g.

The *amount of drug used* in grams is derived as the sum of the difference in drug weight dispensed and returned by kit; when there are tubes missing, assuming all missing tubes were fully used. This principle will be used to calculate the *total amount of drug used*.

The *duration of study treatment* is derived as the time in days from the date of first study drug application to the date of last study drug application. Per day, the number of toilet visits and the number of study drug applications are reported in a subject diary. If diary data is coming from separate diaries on the same day, it will be pooled to obtain the total number of toilet visits for that given day. *Compliant days* are days, where the number of toilet visits does not exceed the number of study drug applications by more than one. *Non-compliant days* are days of the treatment period, where the number of study drug applications is lower than the number of toilet visits minus 1, where the number of study drug applications or the number of toilet visits is missing, and where no diary entry is given. *Overall compliance (%)* is 100 times the number of compliant days divided by the duration of study treatment in days. Treatment compliance will be categorized to less than 80% versus 80% or more and to less than 70% versus 70% or more.

Duration of study treatment, number of compliant and non-compliant days, overall compliance, total amount of drug used, and weekly amount of drug used will be presented by summary tables by treatment group.

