4.2.6 Dosing-regimen

A FTU corresponding to 0.5 g of MC2-25 cream, or MC2-25 vehicle is to be applied on the vulvar region (i.e., the clitoris and periclitoral skin, interlabial sulci, labia minora, posterior fourchette and perineum, anal and perianal skin) after each toilet visit (during day and night) starting on the day of the Baseline visit. This dosing regimen has been chosen to ensure replenishment of Ala-Gln on the vulvar region (as the cream will likely be removed due to wiping after urination) and to counteract any increase in urea concentration e.g., due to insufficient cleaning/wiping of urine residues after toilet visits. This will also counteract any increase in urea due to urinary leakage between toilet visits. Limited information is available on the normal range of urination frequencies in women. However, a recent survey investigating urination frequencies in 2534 healthy women reported reference ranges for urination frequencies between 2-10 times/day and 0-4 times/night (Wyman et al., 2022). Consequently, the maximum number of applications will be 12 per day. Assuming up to

12 toilet visits per day leads to a maximum total daily dose of 6.0 g of MC2-25 cream (3%) corresponding to 0.18 g Ala-Gln per day or 17 mg MC2-25 cream per cm² skin per day (assuming that 6.0 g cream per day will be distributed on a skin area corresponding to two handprints or 358 cm²).

Systemic safety margin for Ala-Gln: Ala-Gln in the form of Dipeptiven® can safely be administered intravenously up to a maximum daily dose of 0.5 g Ala-Gln/kg/day. Under the assumption that an average adult woman weighs around 70 kg this corresponds to a maximum IV dose of 35 g Ala-Gln per day. If all Ala-Gln applied per day as MC2-25 cream was to penetrate into the systemic circulation this would correspond to a systemic safety margin of approximately 200. However, less than 1% of the topically applied Ala-Gln dose was recovered in the receptor fluid (a surrogate for absorption into the systemic circulation) in an in vitro whole human skin penetration trial with Ala-Gln cream (see IB Section 4.3.1.2) which would correspond to a systemic safety margin of approximately 20,000. Whether whole human skin penetration data can be extrapolated to VLS or not can be debated as VLS skin could be argued both to be a deficient or an efficient skin barrier.

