6.1.2 Dosing and administration

MC2-25 cream, or MC2-25 vehicle must be applied after each toilet visit following urination (during day and night) starting on the day of the Baseline visit. The MC2-25 cream, or MC2-25 vehicle should be applied by the patient in a thin saturating layer to the vulvar region (i.e., vulvar region includes clitoris and periclitoral skin, interlabial sulci, labia minora, posterior fourchette and perineum, anal and perianal skin). Approximately one fingertip-unit (FTU), roughly corresponding to 0.5 g cream is to be used after each toilet visit (during night and day). The vulvar region may be gently cleaned with water and dabbed dry with toilet paper or a clean cloth before each application of the trial treatment. Assuming, a maximum of 12 toilet visits are needed over a period of 24 hours, the maximum daily dose is expected to be around 6.0 g. A treatment application manual will be available for patients.

Reference is made to Section 4.2 for the rationale behind the dosing-regimen.

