6.2.2 Formulation, appearance, packaging, and labelling

Sponsor will provide Solural Pharma with the MC2-25 cream and MC2-25 vehicle. The tubes are identical in appearance and packaging.

MC2-25 cream and MC2-25 vehicle will be labelled in accordance with applicable regulatory requirements and Good Manufacturing Practice Guidelines and delivered to the clinics in boxes.

IMP for one patient consists of the following: One box containing 3 boxes with 8 tubes in each adding up to a total of 24 tubes per patient. Labels for the IMP will comply with the legal requirements of the country where the trial is performed and will be printed in the local language(s).

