6.2.3 Product storage and stability

The IMP must be stored securely at the site under the control of the investigator. The temperature will be monitored and documented. The IMP will be supplied to the clinical site(s) as tubes containing 60 g of product. The IMP is to be stored according to the label. At all times, the IMP tube should be protected from direct sunlight exposure.

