## 2 Study Design and Objectives

### 2.1 Study Design

This is a multicentre, phase 2, randomised, double-blind, 2-arm, parallel-group and vehicle-controlled trial in VLS conducted in Denmark. Random allocation to one of two parallel treatment groups is in a 1:1 ratio to MC2-25 cream or MC2-25 vehicle.

A total of 40 patients are planned to be enrolled, randomised and observed until final evaluation and completion. Patients prematurely terminating the trial will not be replaced. Following protocol amendment #3, and the associated protocol v4.0, recruitment was terminated at 33 patients.

The maximum trial duration for each patient will be at most 18 weeks and includes a screening period of up to 4 weeks (allowing for wash out of other treatments and emollients before baseline as/if applicable), a 12-week treatment period, and a 2-week post-treatment follow-up (FU) period.

A total of eleven visits are planned (six of these will be in-clinic, 4 by phone, and the follow-up visit either in-clinic or by phone). The in-clinic visits will be held at Screening 1 (Visit 1, Day -28 to -8), Baseline (Visit 3, Week 0, Day 0), Visits 4, 6, and 8 at Weeks 1, 4 and 8, respectively, planned for Days  $7\pm1$ ,  $28\pm4$ , and  $56\pm4$ , respectively, Visit 10 as end of treatment Visit (Week 12, Day  $84\pm4$ , or at early termination). The follow-up visit at Visit 11 (Week 14, Day  $98\pm4$ ) will be either an in-clinic or a phone visit, depending on the follow up assessments considered necessary by the investigator. The phone visits will be held at Screening 2 (Visit 2, Day -11 to -8), Visits 5, 7, and 9 at Weeks 3, 7 and 11, respectively, planned for Days  $18\pm2$ ,  $46\pm2$ , and  $74\pm2$ , respectively. An unscheduled visit can be conducted to perform any of the post-baseline assessments or procedures included in the schedule of assessments (SoA) if deemed necessary by the Investigator. If Screening 1 visit is performed on Day -8, then Screening 2 visit will be omitted. For a visit schedule, see CTP Section 1.3 [1].

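### SAP 2.4.3 counts every missing tube as fully used, so a box that is never returned is credited as 480 g, about 2.9 times the expected maximum for its period, in the descriptive exposure summaries

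*SAP*

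**What the plan says.** Under SAP 2.4.3 the amount used is the difference between drug weight dispensed and drug weight returned, summed by kit, "when there are tubes missing, assuming all missing tubes were fully used". The total amount follows the same principle, and total and weekly amounts are summarised by treatment group. Returns are scheduled as follows: "Patients will at visit 6, visit 8 and visit 10 be asked to return the dispensed carton box". The section gives no cap, no separate rule for a box that does not come back, and no alternative summary.

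The supply is described in the protocol. Section 6.2.2 states: "One box containing 3 boxes with 8 tubes in each adding up to a total of 24 tubes per patient". Section 6.2.3 gives "tubes containing 60 g of product". The schedule of assessments (Table 1) has dispensing at Baseline, Week 4 and Week 8, and return at Weeks 4, 8 and 12.

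On expected use, protocol 4.2.6 has "A FTU corresponding to 0.5 g of MC2-25 cream" per application and up to 12 applications a day. Section 6.1.2 concludes that "the maximum daily dose is expected to be around 6.0 g".

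**The concern.** The supply is far larger than the expected need, so a tube that is missing is not necessarily an empty one. Treating a discarded empty tube as fully used is sensible. Treating eight tubes in an unreturned box that way credits more cream than the protocol expects anyone to apply.

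The error always runs upward, and it is largest for a patient who stops early in a period and never brings the box back: she has used the least and is credited with the whole box. Protocol 7.3 foresees patients without an End-of-Treatment visit, namely those who withdraw consent or are lost to follow-up.

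At stake is the credibility of the weighed exposure figures. Protocol 9.4.7.1 names total and average weight used among its exposure measures. In arms of 16 to 17, a single unreturned box shifts the mean, inflates the SD and is likely to set the maximum. If unreturned boxes differed between arms, the difference would look like a difference in exposure.

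**Working it through.** **Inputs**

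| Quantity | Value | Source |
|---|---|---|
| Content of a tube | 60 g | Protocol 6.2.3 |
| Tubes per box; boxes per patient | 8; 3 | Protocol 6.2.2 |
| Dispensing visits | Baseline, Weeks 4 and 8 | Protocol Table 1 |
| Return visits | 6, 8 and 10 (Weeks 4, 8 and 12) | SAP 2.4.3; timing in SAP 2.1 |
| Amount per application | 0.5 g | Protocol 4.2.6 |
| Maximum applications per day | 12 | Protocol 4.2.6 |
| Patients per arm | 16 to 17 | Protocol 9.2 |

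**Step 1. Reproduce the plan's figures.** Daily maximum: 12 x 0.5 g = 6.0 g, as stated. Supply: 3 x 8 = 24 tubes, as stated.

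**Step 2. Credit for an unreturned box.** Three boxes, three dispensing visits and three return visits imply one box per interval of nominally 28 days. The credit is 8 x 60 g = 480 g.

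**Step 3. Expected maximum for the period.** 28 x 6.0 g = 168 g. The ratio is 480/168 = 2.86. The credit amounts to 480/28 = 17.1 g a day, or 17.1/0.5 = about 34 applications a day. Per week it is 480/4 = 120 g, against 7 x 6.0 = 42 g.

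**Step 4. Vary the length of the period.** With visits at Day 28 ± 4, 56 ± 4 and 84 ± 4, the first box covers 24 to 32 days and the later boxes 20 to 36 days. The last two rows show a patient who stops early within a period.

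| Days of use | Expected maximum (6.0 g x days) | 480 g divided by it |
|---|---|---|
| 20 | 120 g | 4.0 |
| 24 | 144 g | 3.3 |
| 28 | 168 g | 2.9 |
| 32 | 192 g | 2.5 |
| 36 | 216 g | 2.2 |
| 14 (stops early) | 84 g | 5.7 |
| 7 (stops early) | 42 g | 11.4 |

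**Step 5. How many tubes should be empty?** At the expected maximum, 168/60 = 2.8 tubes per 28 days, so fewer than 3 of 8. One missing tube counted as full adds 60/6.0 = 10 days of maximum use.

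**Step 6. Effect on an arm mean.** The shift from one patient with one unreturned box is (480 - true use)/n.

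| True use in the period | n = 16 | n = 17 |
|---|---|---|
| 168 g (expected maximum) | 19.5 g | 18.4 g |
| 84 g | 24.8 g | 23.3 g |
| 0 g | 30.0 g | 28.2 g |

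**Net or gross weight.** These figures use the 60 g net content. SAP 2.4.3 prints only gross weights (73.928 g for a full labelled tube) and no empty-tube weight. If gross tube weights were used without correction, the credit would be 8 x 73.928 = 591.4 g, and 591.4/168 = 3.5 times.

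**The case against.** The strongest reply is that the rule is meant for a box that comes back a tube short, where assuming that the missing tube was emptied is reasonable. SAP 2.4.3 describes weighing a returned box and gives a per-tube weight for this purpose. It never mentions a box that is wholly unreturned. This is a fair account of the intent. As written, however, the rule covers all missing tubes and nothing else applies when all eight are missing, so a programmer following the SAP would credit 480 g.

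The reply is also right about reach. Overall compliance, and with it the 80% threshold named for the per-protocol set, comes from diary counts of applications and toilet visits, not from weights. The while-on-treatment analysis depends on the timing of the last treatment. No planned safety table uses grams. The amounts appear in one descriptive table (14.1.9) and in listings. The planned quartiles and range, and the listings of returned IMP and exposure, would let a careful reader find an outlier.

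Three stronger readings are tempting and are not supported.

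- A reader might infer that unreturned boxes belong mainly to patients who are lost or withdrawn. The documents do not say so. Protocol 7.1 asks for the Week 12 assessments as far as possible after withdrawal or discontinuation, and IMP return is scheduled at that visit. No dropout rate is given.
- A reader might infer that the credited amount is impossible. The 6.0 g is an expected maximum, worded as approximate, and not a cap.
- A reader might infer that the efficacy or safety conclusions are biased. For the reasons above, they are not.

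**Conclusion.** The point holds as a defect in the rule for descriptive exposure. Followed literally, SAP 2.4.3 credits a wholly unreturned box as 480 g, about 2.9 times the expected maximum for a 28-day period. The range is about 2.2 to 4.0 across visit windows, and it is higher when the patient stopped early in the period. One such patient raises the mean total of an arm by about 18 to 30 g.

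This rests on four assumptions: one box per four-week interval, which is inferred from the supply and the schedule and not stated in one sentence; the net 60 g reading of a tube; 6.0 g a day as an approximate maximum; and the rule being applied to a whole box because no other rule exists. How many boxes will be unreturned is unknown and may be none. The change is worth making because the direction of the error is known and the correction is cheap.

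**What to change.** Amend SAP 2.4.3 before unblinding.

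- **Wholly unreturned box:** set the weighed amount for that period to missing. Where the application diary for the period was returned, the amount may be estimated as recorded applications x 0.5 g, labelled as an estimate. This cannot be the general remedy, because the diary and the box are due back at the same visit and will often be lost together.
- **Isolated tubes missing from a returned box:** the fully-used assumption may stay. Label the result as an upper bound, and show total and weekly amounts with and without those periods. Simply dropping the periods would remove patients who threw away an emptied tube, who may be the heavier users.
- **Reporting:** give the number of unreturned boxes and unreturned tubes by arm. State whether a patient's total is missing when one period is missing, or is the sum over weighed periods with the days covered.

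The cost is a short SAP edit and a small programming change. The downside is that a few patient-periods will have no weighed amount.
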